2 ELIGIBILITY ASSESSMENT AND ENROLLMENT

2.1 ELIGIBILITY CRITERIA

2.1.1 Inclusion Criteria for All Subjects

2.1.1.1 Histopathological documentation of prostate cancer confirmed in either the Laboratory of Pathology at the National Institutes of Health (NIH) Clinical Center, or Walter Reed National Military Medical Center prior to enrollment. If no pathologic specimen is available, participants may enroll with a pathologist's report showing a histologic diagnosis of prostate cancer and a clinical course consistent with the disease.

2.1.1.2 Recovery to baseline from acute toxicity related to prior therapy, including surgery and radiation (28 days removed from last systemic therapy, 14 days removed from last radiation therapy).

- Hepatic function eligibility parameters (within 16 days before starting therapy):
 - Bilirubin \leq ULN (OR in participants with Gilbert's syndrome, a total bilirubin \leq 3.0), AST and ALT \leq 1.5 times upper limit of normal.

2.1.1.3 Adequate renal function defined by an estimated creatinine clearance > 50 mL/min according to the Cockcroft-Gault formula or by measure of creatinine clearance from 24 hour urine collection.

2.1.1.4 No other active malignancies within the past 36 months (with the exception of nonmelanoma skin cancers or carcinoma in situ of the bladder) or life-threatening illnesses.

2.1.1.5 Willing to travel to the NIH for follow-up visits.

2.1.1.6 18 years of age or older.

2.1.1.7 Able to understand and sign informed consent.

2.1.1.8 The effects Prostvac and CV301 on the developing human fetus are unknown. For this reason, men must agree to use highly effective contraception (that is, methods with a failure rate of less than 1% per year) prior to study entry, for the duration of study therapy and at least four months after the last treatment administration. Should a woman become pregnant or suspect she is pregnant while her partner is participating in this study, she should inform her treating physician immediately.

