- 2.1.4.14 History of atopic dermatitis or active skin condition (acute, chronic, exfoliative) that disrupts the epidermis
- 2.1.4.15 Unable to avoid close contact or household contact with the following high-risk individuals for three weeks after the Day 1 vaccination: (a) children ≤ 3 years of age, (b) pregnant or nursing women, (c) individuals with prior or concurrent extensive eczema or other eczemoid skin disorders, or (d) immunocompromised individuals, such as those with HIV.
- 2.1.4.16 Participants who test positive for HBV or HCV
- 2.1.4.17 Clinically significant cardiovascular/cerebrovascular disease as follows: cerebral vascular accident/stroke (< 6 months prior to the first planned dose of study drugs), myocardial infarction (< 6 months prior to the first planned dose of study drugs), unstable angina, congestive heart failure (New York Heart Association Classification

Class \geq II), serious cardiac arrhythmia, or uncontrolled hypertension (SBP>170/DBP>105).

2.1.4.18 Participants who have received a red cell transfusion within 2 weeks prior to enrollment.

2.1.4.19 Participants unwilling to accept blood products as medically indicated.

2.1.4.20 Individual tumor lesion(s) in the liver or chest which are 10 cm or larger.

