2.4 BASELINE EVALUATION

- A. The following parameters will be obtained **within 8 weeks** prior to enrollment:
 1. Baseline electrocardiogram (EKG) on all participants, and appropriate cardiologic evaluation, as clinically indicated, to provide baseline function and identify any participants who should be monitored closely for cardiac risks associated with vaccinia vaccination.
- B. The following parameters will be obtained **within 16 days** prior to start of treatment (these tests will not need to be repeated if they were done at screening within the appropriate timeframe):
 1. Clinical evaluation
 - History and physical examination

- ECOG performance status (see **APPENDIX A**)
- Height, weight

2. Laboratory studies

- Serum PSA
- Serum testosterone level
- CBC/differential, with platelet count
- Serum chemistries (Na⁺, K⁺, Cl⁻, CO₂, glucose, BUN, creatinine, albumin, calcium, magnesium, phosphorus, alkaline phosphatase, ALT, AST, total bilirubin, LDH, CK, uric acid, total protein)
- Serum amylase and lipase
- Serum thyroid stimulating hormone (TSH)
- Lymphocyte phenotyping CD3/CD4/CD8
- Urinalysis in participants unless not feasible (i.e.. participant has incontinence)
- Prostate acid phosphatase (PAP)

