3.4 PROTOCOL EVALUATION

NOTE: Also see **APPENDIX C**.

- All participants who are deemed eligible and who sign an informed consent will be enrolled in this trial.
- A complete history and physical examination, including ECOG performance status, will be done within 16 days before enrollment.
- Laboratory Studies (See also **APPENDIX C**)
 - Serum PSA
 - CBC/differential with platelet count
 - Serum testosterone level
 - Serum chemistries (Na^+ , K^+ , Cl^- , CO_2 , glucose, BUN, creatinine, albumin, calcium, magnesium, phosphorus, alkaline phosphatase, ALT, AST, total bilirubin, LDH, CK, uric acid, total protein)
 - Serum amylase and lipase
 - Serum thyroid stimulating hormone (TSH)

- HIV/Hepatitis B/Hepatitis C tests (within 8 weeks prior to start of enrollment)
- Lymphocyte phenotyping CD3/CD4/CD8
- PAP (prostatic acid phosphatase)
- Urinalysis unless not feasible (i.e., participant has incontinence)

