6 DATA COLLECTION AND EVALUATION

6.1 DATA COLLECTION

- Eligible participants must be confirmed and checklist completed. Consent form must be signed prior to registration with Central Registration Information Services.
- Data will be secured in a 21 CR-Part 11-compliant data capture system provided by the NCI CCR. Data will be collected using protocol-specific case report forms, and verified for accuracy and completeness. Hard copies of data will be stored in locked secured areas and data will be entered onto a secured electronic data base. The following protocol-specific study forms will be complete and stored: eligibility checklist (developed by Central Registration Office, CRO). A copy of all serious AE forms will be kept in the research record.
- Treatment is given according to protocol (dated notes about doses given, complications, and clinical outcomes).
- Toxicity is assessed according to protocol (laboratory report slips, etc.)
- Response is assessed according to protocol (X-ray, scan, lab reports, and date noted on clinical assessment, as appropriate).
- Drug Accountability Records are kept for each participant.

The PI will be responsible for overseeing entry of data into a 21 CR-Part 11-compliant data capture system provided by the NCI CCR and ensuring data accuracy, consistency and timeliness. The principal investigator, associate investigators/research nurses and/or a contracted data manager will assist with the data management efforts. Primary and final analyzed data will have identifiers so that research data can be attributed to an individual human subject participant.

All adverse events, including clinically significant abnormal findings on laboratory evaluations, regardless of severity, will be followed until return to baseline or stabilization of event.

Document AEs from the first study intervention, Study Day 1, through 28 days after last dose of study treatment.

An abnormal laboratory value will be considered an AE if the laboratory abnormality is characterized by any of the following:

- Results in discontinuation from the study
- Is associated with clinical signs or symptoms
- Requires treatment or any other therapeutic intervention
- Is associated with death or another serious adverse event, including hospitalization.
- Is judged by the Investigator to be of significant clinical impact

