The CDC is the only source of the licensed vaccinia vaccine. The CDC will provide vaccinia vaccine to protect laboratory and other healthcare personnel, whose occupations place them at risk of exposure to vaccinia and other closely related orthopoxviruses, including vaccinia recombinants. The vaccine should be administered under the supervision of a physician selected by the study institution. Revaccination is recommended every 10 years. For instructions on obtaining the licensed vaccinia vaccine, contact Drug Services, National Center for Infectious Diseases, CDC at [contact].

Recombinant Vaccinia Vaccine Participant Care Implications, Contraindications and Potential Complications

Participant Care Implications and Contraindications

Cover vaccination sites with a sterile dry dressing (e.g., Telfa pad). Instruct participants on proper hand-hygiene, sterile dressing care, bathing, laundering of clothing, *etc.* Treat participant bandages or dressings removed from the vaccination site as infectious waste and dispose in appropriate biohazard containers. Do not administer the recombinant vaccinia vaccine if the recipient, or for at least three weeks after vaccination, their close household contacts (close household contacts are those who share housing or have close physical contact):

- have active eczema or a history of eczema or atopic dermatitis, or Darier's disease.
- have other acute, chronic, or exfoliative skin conditions (e.g., burns, impetigo, varicella zoster, severe acne, contact dermatitis, psoriasis, herpes or other open rashes or wounds), until the condition resolves.
- are pregnant or intend to become pregnant (due to the potential risk of fetal vaccinia); or are breast-feeding (due to the potential risk of contact transmission and inadvertent inoculation). It is currently unknown if vaccinia virus or antibodies are excreted in breast milk. Participants (*i.e.*, vaccinees) should avoid fathering a child for at least 4 months following completion of therapy with the recombinant vaccine.
- are in close contact with children less than 3 years of age (due to the potential risk of contact transmission and inadvertent inoculation).
- are immunodeficient or immunocompromised (by disease or therapy), including individuals with HIV infection.

Additionally, do not administer the recombinant vaccinia vaccine if the vaccinee:

- has a moderate or severe acute illness, until the illness resolves.

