- is undergoing topical steroid therapy for inflammatory eye diseases, or undergoing therapy with systemic steroids; potential immune suppression increases risk for vaccinia-related complications.
- At this time, until a more definitive causal relationship is determined, it is recommended that participants with known CHF or clinically significant cardiomyopathy, not be vaccinated with recombinant vaccinia-based vaccines, due to the potential for development of myocarditis and/or pericarditis.

Although the CDC believes that there is no evidence to conclude that the licensed vaccinia vaccine used in the Smallpox Vaccination Program causes angina or heart attacks, it acknowledges a possible causal relationship between the vaccination and heart inflammation. The CDC continues to study the relationship, but in the meantime, recommends excluding individuals with underlying heart disease from participation in the current Smallpox Vaccination Program. Participants are being immunized with recombinant vaccinia vaccines with therapeutic intent and will be evaluated for cardiovascular risk factors and recent or symptomatic cardiac events per protocol eligibility criteria. Participants will be encouraged to minimize cardiovascular disease risks and encouraged to follow risk reduction according to standard medical practice.

Due to the method of manufacturing (virus grown in primary chicken embryo dermal cells), do not administer the recombinant vaccinia vaccine to participants with a history of allergy to eggs or

egg products. Do not administer the recombinant vaccinia vaccine to participants with a history of allergy or serious reaction to prior vaccinia vaccination (e.g., smallpox vaccination).

Potential Complications Associated with Recombinant Vaccinia Vaccination

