and myopericarditis. Although the CDC believes that there is no evidence to conclude that the licensed vaccinia vaccine causes angina or heart attacks, it acknowledges a possible causal relationship between the vaccination and heart inflammation. The CDC continues to study the relationship, but in the meantime, recommends that individuals with underlying heart disease be excluded from participation in the current Smallpox Vaccination Program. While it is currently not possible to fully evaluate the risk of cardiac events or the risk of myocarditis, pericarditis, or myopericarditis associated with vaccinia vaccination, it is reasonable to inform patients participating in studies using recombinant vaccinia virus of these reports and provide relevant guidance for evaluating these events. Further investigation from the ongoing vaccine program may provide additional data regarding an association or lack of association with cardiovascular disease. Patients are being immunized with recombinant vaccinia vaccines with therapeutic intent and will be evaluated for cardiovascular risk factors and recent or symptomatic cardiac events per protocol eligibility criteria. Patients will be encouraged to minimize cardiovascular disease risks and encouraged to follow risk reduction according to standard medical practice. At this time the evidence for an association with myocarditis, pericarditis, or myopericarditis seems plausible, but a rare event. If not otherwise excluded, patients with known CHF or clinically significant cardiomyopathy requiring treatment should be excluded from protocol eligibility.

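### The cardiac exclusion in 2.1.4.17 is narrower than 14.2.7: it starts heart failure at NYHA class II and omits cardiomyopathy, so Section 2.1 admits men whom the product section says to exclude

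*Combined protocol and SAP*

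**What the plan says.** Section 2.1.4.17 excludes clinically significant cardiovascular or cerebrovascular disease and then specifies what counts. Six conditions are named: recent stroke, recent myocardial infarction, unstable angina, heart failure, serious arrhythmia and uncontrolled hypertension. The heart failure entry reads "unstable angina, congestive heart failure (New York Heart Association Classification" and continues with class II or higher. Cardiomyopathy is not among the six.

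Section 14.2.7 returns to the subject twice. Among the contraindications for the vaccinee, "it is recommended that participants with known CHF or clinically significant cardiomyopathy, not be vaccinated with recombinant vaccinia-based vaccines". In its item on myocarditis and pericarditis it goes further: "If not otherwise excluded, patients with known CHF or clinically significant cardiomyopathy requiring treatment should be excluded from protocol eligibility". Neither sentence sets an NYHA threshold.

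Section 2.4 requires a baseline ECG, with cardiologic evaluation as clinically indicated, partly to "identify any participants who should be monitored closely for cardiac risks associated with vaccinia vaccination". Section 3.4 states "All participants who are deemed eligible and who sign an informed consent will be enrolled in this trial", and Section 6.1 adds "Eligible participants must be confirmed and checklist completed".

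**The concern.** Section 2.1 is where staff look to decide whether a man may enter. If the product section says a cardiac condition should make him ineligible and the eligibility list lets him through, the protocol holds two eligibility standards and the weaker one sits in the operative place.

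What is at stake is the safety of a small group. Prostvac-V is a live vaccinia vector which, according to 14.2.1, can replicate in mammalian cells. Section 14.2.7 acknowledges a possible causal link between vaccinia vaccination and heart inflammation. These men have biochemical recurrence only, and Section 1.2.8 notes that they may live another decade.

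**Working it through.** There is no planned figure to reproduce. The check sets the texts side by side.

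**Step 1: who passes 2.1.4.17 but is caught by 14.2.7.** In the item on myocarditis and pericarditis, the words about requiring treatment can attach to cardiomyopathy alone (reading A) or to heart failure as well (reading B). Assume the man has none of the other conditions in 2.1.4.17.

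| Condition | 2.1.4.17 | 14.2.7, reading A | 14.2.7, reading B |
|---|---|---|---|
| Class I heart failure, treated | passes | exclude | exclude |
| Class I heart failure, untreated | passes | exclude | recommendation against vaccination only |
| Significant cardiomyopathy, treated, no class II+ failure | passes | exclude | exclude |
| Significant cardiomyopathy, untreated, no class II+ failure | passes | recommendation against vaccination only | recommendation against vaccination only |

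The first and third rows conflict on either reading.

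**Step 2: whether another criterion closes the gap.**
- Of the 20 exclusion items, 2.1.4.1 to 2.1.4.20, none names cardiomyopathy and none cites Section 14.
- 2.1.1.4 requires no other active malignancies, with exceptions ending "carcinoma in situ of the bladder) or life-threatening illnesses". The last part may catch severe cardiomyopathy, but not stable treated disease.
- 2.1.4.4 depends on the investigator's judgment and asks whether an illness would interfere with carrying out treatment. It does not ask about vaccinia cardiac risk.
- ECOG 0 to 1 (2.1.3.4) does not name these conditions, and a man with class I failure could meet it.
- The work-up in 2.4 serves to identify men for closer monitoring. It states no rule that excludes them.

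**Step 3: exposure.** Prostvac-V is given once, on C1D1. The accrual ceiling is 40. Taking out Arm 1 and Arm 2 leaves 40 − 6 − 6 = 28 men at most in Arm 3, of whom 25 evaluable are planned. Arm 3 takes men enrolled after approval of the 7/29/2021 amendment, and this version is dated 05/10/2023, so some may already have been dosed. The number is not stated.

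**Step 4: background rates in 14.2.7.**
- Military vaccinees: 67 / 540,824 = 1.2 per 10,000 with symptomatic myopericarditis.
- Health care workers: 21 / 37,901 = 5.5 per 10,000 with myocarditis or pericarditis, described as mild and with no deaths.

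These are not rates in people with heart failure or cardiomyopathy, so they give context and do not estimate the risk in the gap group.

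**Step 5: neighbouring wording.** For recipients and their close household contacts, 14.2.7 bars vaccinia if they "have active eczema or a history of eczema or atopic dermatitis, or Darier's disease". Section 2.1.4.14 covers a history of atopic dermatitis and any active condition that breaks the epidermis. What remains is past non-atopic eczema and Darier's disease without active lesions. Section 14.2.7 also bars dosing during any systemic steroid therapy, whereas 2.1.4.3 and 4.1 bar only use beyond 14 days. For eye steroids there is no net gap, because 4.1 already prohibits them around Prostvac-V.

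**The case against.** The best reply is that the two sections add to each other. The sentence in 14.2.7 opens by addressing men not otherwise excluded, so it expects the main list to miss some and supplies the remainder. Section 14 is part of the same protocol, a man it excludes is not eligible, and the enrolment sentence in 3.4 therefore does not reach him. This is right as a matter of interpretation, and it makes the problem one of placement. It does not remove the problem: 2.1.4.17 still gives a specific threshold that differs from 14.2.7, with no cross-reference and no reason for the difference.

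It can also be said that 14.2.7 defers to the eligibility criteria for cardiac screening. It does, but the item on myocarditis and pericarditis states that screening and then adds the exclusion, so the exclusion goes beyond it.

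Several stronger inferences are tempting and are not supported:
- **That the eligibility checklist repeats the gap.** Section 6.1 says only that a checklist is completed and was developed by the registration office. Its content is not shown.
- **That the stricter rules appear only in the product section.** Appendix B, the vaccinia instruction sheet that 3.2.1 requires at or before dosing, was not available for review.
- **That the skin wording is a separate safety defect.** The remaining skin group is narrow, and 14.2.7 already forbids giving these men the dose.
- **That short steroid courses are an eligibility gap.** A short course is temporary and calls for deferral. Concomitant medications are already reviewed at C1D1.
- **That 3.3.2 would turn a deferred C1D1 into a missed dose.** This is doubtful. C1D1 starts the treatment schedule, and the calendar notes in 18.1 let surveillance visits slip by up to two weeks.

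**Conclusion.** The cardiac inconsistency holds and should be fixed. Section 2.1 admits at least two groups whom 14.2.7 says to exclude: men with treated class I heart failure, and men with treated, clinically significant cardiomyopathy who do not have class II or higher failure. This does not depend on how the treatment qualifier is read. It assumes that Section 2.1 is applied as written and that no general criterion happens to remove the man.

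The size is modest. The documents give no prevalence for these conditions, so no probability is offered. Arm 3 is capped at 28 men, an unstated number of whom have already been dosed, and 14.2.7 regards the cardiac association as plausible but rare. The skin and steroid differences are minor alignment. Nothing here touches the sample size, the power or the reading of the PSA response.

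**What to change.** Amend 2.1.4.17 so that it excludes known congestive heart failure of any NYHA class and clinically significant cardiomyopathy requiring treatment. Apply the change to men not yet given Prostvac-V, and update the eligibility checklist if it does not already carry the rule.

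In the same amendment, as tidying, add a history of eczema and Darier's disease to 2.1.4.14. Note in 4.1 or 3.2.1 that Prostvac-V is deferred while a man is on systemic steroids, as 14.2.7 already requires.

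The cost is a few lines of text. No visit or test is added: the baseline ECG and the history and physical in 2.4, and the C1D1 history and medication review in 18.1, are already scheduled. The downside is that a few men become ineligible.

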2.1.5 Recruitment Strategies

This protocol may be abstracted into a plain language announcement posted on NIH websites and on NIH social media platforms. This study will be listed on available websites (www.clinicaltrials.gov, <https://www.cancer.gov/about-cancer/treatment/clinical-trials/search>) and participants will be recruited from the current patient population at NIH.

2.2 SCREENING/ELIGIBILITY EVALUATION

Note: Screening evaluation testing/procedures are conducted under the separate screening protocol, 01-C-0129 (Eligibility Screening and Tissue Procurement for the NIH Intramural Research Program Clinical Protocols).

A. Pathological confirmation of diagnosis by either the Laboratory of Pathology at the NIH or Walter Reed National Military Medical Center may be obtained any time prior to enrollment (if specimen is available). If no pathologic specimen is available, participants may enroll with a pathologist's report showing a histologic diagnosis of prostate cancer and a clinical course consistent with the disease.

B. The following parameters will be obtained within 8 weeks prior to start of enrollment:

1. HIV test (anti-HIV 1/2 antibody)
2. Hepatitis B and C (HBs AG screening and anti-HCV antibody)
3. Tc-99 whole-body scintigraphy
4. CT (or MRI may be substituted at investigator's discretion) of chest, abdomen and pelvis

C. The following parameters will be obtained within 16 days prior to start of enrollment:

1. History and physical examination with ECOG
2. Serum PSA
3. Complete blood count plus differential, and platelet count
4. Hepatic Panel (Alkaline Phosphatase, ALT/GPT, AST/GOT, Total Bilirubin, Direct Bilirubin)
5. Acute Care Panel (Sodium [NA], Potassium [K], Chloride [CL], Total CO₂ [Bicarbonate], Creatinine, Glucose, Urea Nitrogen, eGFR)
6. Testosterone level
7. 24-hour urine collection if creatinine clearance to be confirmed by this method

